3.2 Study Population

Approximately 46 subjects will be enrolled in Part 1 of the study (18 subjects for 13 to 17-year-old cohort, 14 subjects for 8 to 12-year-old cohort, and 14 subjects for 4 to 7-year-old cohort).

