5.5 Study Drug Exposure

For each subject, information regarding study drug exposure will be derived from the eCRF and study drug dosing eDiary data. Here is a summary:

- First dose date is defined as the date the first study drug dose is taken, as shown in the eCRF ('AFREZZA[®] dosing' page at Visit 2).
- Last dose date is defined as the date the last study drug dose is taken, as shown in the eDiary.
- Period-specific treatment start date:
 - Treatment start date in the titration period is defined as Study Day 1.
 - Treatment start date in the extension period is defined for subjects who participate in the extension period only, as the date the first study drug dose is taken after the date of Visit 15.
- Period-specific treatment end date:
 - Treatment end date in the titration period is defined as:
 - The date the last study drug dose is taken, for subjects who do not participate in the extension period;
 - The date the last study drug dose is taken prior or on the date of Visit 15, for subjects who participate in the extension period
 - Treatment end date in the extension period is defined for subjects who participate in extension period only, as the date the last study drug dose is taken.
- Total Exposure time (days) is defined as last study dose date – first study dose date +1.
- Period-specific exposure time (days) is defined as period-specific treatment end date – period-specific treatment start date +1.
- Total daily dose is defined as the sum of all doses of AFREZZA[®] taken during a day.
- Prandial dose at a meal is defined as the sum of the pre-meal dose and the post-meal dose given at that meal. Per protocol, subjects should take a dose at beginning of each meal, and the post-meal dose will be given as needed to keep the blood glucose level in control.

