8.3 Safety Analyses

8.3.1 Adverse Event

Definition

Adverse Event (AE)

An AE is any untoward medical occurrence in a subject administered a pharmaceutical product and which does not necessarily have to have a causal relationship with this treatment. An AE can be any unfavorable and unintended sign (e.g., an abnormal laboratory finding), symptom, or disease temporally associated with the use of a drug, and does not imply any judgment about causality.

General

All adverse events will be described with cohort, start date, resolution date, seriousness, severity (mild, moderate, severe), outcome of AE (recovered/resolved, recovering/ resolving, recovered/resolved with sequelae, not recovered/resolved, death related to AE, and unknown), relationship to study treatment (definite, probable, possible, unlikely, and not related), action taken with investigational medicinal product (dose increased dose, dose not changed, dose reduced, dose interrupted, dose withdrawn, not applicable, and unknown), other action taken (treatment given and withdrawn from the trial).

Coding

Adverse events will be coded by the system organ class and preferred terms specified in the MedDRA (version 20.1) dictionary.

Classification

Prior Adverse Event

A prior adverse event is defined as adverse event whose start date is before the date of the first dose of study drug.

A subject listing will be presented for all the prior adverse events.

Treatment-Emergent Adverse Event (TEAE)

An adverse event is treatment-emergent if the start date is on or between the date of the first dose of study drug and the date of the last dose of study drug plus 30 days (inclusive). Worsening of a pre-treatment event during the trial is also treatment emergent.

Follow-up Adverse Event

A follow-up adverse event is defined as adverse event whose start date is between the date of the last dose of study drug plus 30 days (exclusive) and the date of the last visit day of the follow-up period.

A subject listing will be presented for all the follow-up adverse events.

Special Adverse Event

The following special treatment-emergent adverse event will be identified and reported from the adverse event database.

- Acute bronchospasm
- Verified clinically relevant decline in pulmonary function
- Hypersensitivity reactions, including anaphylaxis, which can occur with insulin products, including AFREZZA
- Diabetic ketoacidosis

Serious Adverse Event

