8.3.3 Hypoglycemic Event

Definitions:

Hypoglycemic event:

The general symptoms of hypoglycemia most subjects experience include 1 or more of the following: headache, dizziness, general feeling of weakness, drowsiness, confusion, pallor, irritability, trembling, sweating, lightheadedness, shaky, increased appetite, rapid heartbeat and a

cold, clammy feeling. In severe cases, seizure, loss of consciousness, or even coma can occur.

All hypoglycemic events will be recorded on the Hypoglycemia eCRF page. In addition, severe hypoglycemia episodes and other hypoglycemia episodes which meet the criteria of SAE will also be records as SAEs in the AE page and safety complementary e-CRF.

Non-severe Hypoglycemic event

Non-severe hypoglycemic event is defined according to the ISPAD Clinical Practice Consensus Guidelines 2014 (3) as follows:

- SMBG levels <70 mg/dL and/or
- Symptoms of hypoglycemia that are relieved by the administration of carbohydrates

Severe Hypoglycemic event

Severe hypoglycemic event in children is defined according to the ISPAD Clinical Practice Consensus Guidelines 2014 (3) as an event associated with a seizure, coma, or loss of consciousness and will be considered an SAE.

Asymptomatic Hypoglycemic event

Asymptomatic hypoglycemic event is defined as an episode not accompanied by typical symptoms of hypoglycemia, but with a measured plasma glucose concentration < 70 mg/dL

Symptomatic hypoglycemic event

Symptomatic hypoglycemic event is defined as an episode accompanied with typical symptoms of hypoglycemia, with or without measured plasma glucose concentration, which is relieved by the administration of carbohydrates

Nocturnal hypoglycemic event

Nocturnal hypoglycemic event is defined as a hypoglycemia episode which occurs overnight during sleep.

Documented hypoglycemic event

Documented hypoglycemic event is defined as an episode with measured plasma glucose concentration <70 mg/dL. If such an episode is also accompanied by typical hypoglycemic symptoms, then it is defined as a symptomatic documented hypoglycemic event; otherwise, it is defined as an asymptomatic documented hypoglycemic event.

Table Presentation

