Summary tables will be reported by cohort and study period (titration period, extension period, and entire study). Only hypoglycemic events occurred on treatment (i.e., with start date between the first dose date and last dose date, both inclusive) will be included. Number and percentage of subjects with hypoglycemic events, number of hypoglycemic events, and event rate in subject-month accounting for observation time will be presented for the following categories:

- All hypoglycemic events
- Asymptomatic hypoglycemic events
- Symptomatic hypoglycemic events
- Nocturnal hypoglycemic events
- Severe hypoglycemic events
- Documented hypoglycemic events
- Symptomatic documented hypoglycemic events
- Asymptomatic documented hypoglycemic events

For percentage calculation, number of subjects in each cohort in the safety population will be used as denominator for the summaries for the entire study and the titration period. For the extension period, number of subjects in safety population who participate in extension period will be used as denominator.

For calculation of event rate, observation time is defined as treatment exposure time (total exposure time and period-specific exposure time for the corresponding analysis respectively, see definition in Section 5.5).

In addition, causality of hypoglycemic events will be summarized (for the entire study only). Number and percentage of subjects experiencing hypoglycemic events in each causality category will be presented by cohort.

Graphical Presentation

Only hypoglycemic events occurred on treatment will be included. The following graphs will be presented by cohort and overall:

- Day profile of hypoglycemic events

Event rate (in subject-month) will be calculated at 1 week interval for the titration period and at 1 month interval the extension period, and plotted against time since the start of the study period. Onset date of the event will be used to determine the time interval. Weeks since the start of the study period will be calculated as $\text{int}((\text{date} - \text{start date of the study period} + 1) / 7)$. Months since the start of the period will be calculated as $\text{int}((\text{date} - \text{start date of the study period} + 1) / 30.4375)$.

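### The on-treatment window for hypoglycaemia closes at midnight on the last dose date, so an overnight episode after the final evening dose is left out of the hypoglycaemia table

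*SAP*

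**What the plan says.** SAP 8.3.3 includes in the hypoglycaemia summaries only events "with start date between the first dose date and last dose date, both inclusive", and applies the on-treatment restriction again to the figures. SAP 5.5 fixes the two limits by date: "First dose date is defined as the date the first study drug dose is taken, as shown in the eCRF" and "Last dose date is defined as the date the last study drug dose is taken, as shown in the eDiary". No clock time enters either definition, and no section adds time after the last dose.

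Nocturnal episodes are a row of the table: "Nocturnal hypoglycemic event is defined as a hypoglycemia episode which occurs overnight during sleep". For percentages, "number of subjects in each cohort in the safety population will be used as denominator" (entire study and titration period). For rates, "observation time is defined as treatment exposure time", counted in whole days.

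Two other parts of the SAP treat time differently. The TEAE window in 8.3.1 runs to 30 days after the last dose. The time-profile figure in 8.3.3 looks up to 4 hours after each pre-meal dose and so needs event times as well as dose times.

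**The concern.** AFREZZA is taken at dinner. A follow-on dose may come 120 to 150 minutes later (Protocol 8.1.4 and 8.1.5), and snack doses are possible (8.1.6). The hours after an evening dose can therefore run past midnight. While the child keeps dosing, the date rule does no harm, because the next dose moves the last dose date past the event. Only the final night is exposed, and that is the night when an episode may itself be the reason for stopping.

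The summary table would then omit an event that is informative about tolerability. Table 14.3.2.1 goes to the DMC (SAP Appendix 3), and the cohorts are small enough for one child to change a percentage visibly.

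**Working it through.** The plan gives no figure for this rule, so the check applies it to examples and then sizes one misclassified child.

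**1. The rule applied.** The first dose is on Day 1 at 08:00, the indicative time in SAP Table 3. The last dose is assumed to be on Day 12 at 21:30.

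| Episode | Position | SAP date rule | Date-time rule, 4 h or 24 h tail | TEAE window, if reported as an AE |
|---|---|---|---|---|
| Day 1, 01:00 | 7 h before first dose | counted | not counted | counted |
| Day 1, 09:30 | 1.5 h after first dose | counted | counted | counted |
| Day 12, 23:50 | 2.3 h after last dose | counted | counted | counted |
| Day 13, 00:40 | 3.2 h after last dose | **not counted** | counted | counted |

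The last two episodes are 50 minutes apart after the same dose and are classified differently.

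**2. How late the dose must be.** With the SAP's own 4-hour span, any last dose after 24:00 − 4 h = 20:00 has risk time past midnight. If that span is extended to follow-on doses (my extension; the SAP applies it to pre-meal doses), the dinner dose need only be later than 20:00 − 120 min = 18:00, or 20:00 − 150 min = 17:30. With the roughly 180 minutes to near-baseline insulin that SAP 1.1 gives for adults, the last dose must be after 21:00.

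**3. Which outputs lose the event.**
- Table 14.3.2.1: the all-events row, the nocturnal row, and the severe row if applicable.
- Table 14.3.2.2 (causality) and Figure 14.3.1.1 (day profile).
- Figure 14.3.1.2 (time profile): the date rule is the reason only if the event falls within 4 hours of a pre-meal dose. Otherwise that figure would omit it anyway.

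**4. Which outputs keep it.**
- Listing 16.2.7.10 (all events) and, if severe, Listing 16.2.7.11. Both go to the DMC.
- A severe episode is by definition an SAE on the AE page. It enters Tables 14.3.1.2 and 14.3.1.6, both sent to the DMC, with subjects, percentage, events and rate.
- A non-severe episode goes on the hypoglycaemia page (Protocol 10.2.4.2). Unless also reported as an AE, it reaches no summary table.

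**5. Size.** Planned cohorts (SAP 3.2) are "18 subjects for 13 to 17-year-old cohort, 14 subjects for 8 to 12-year-old cohort, and 14 subjects for 4 to 7-year-old cohort".
- Percentage of subjects: 1/18 = 5.6 points; 1/14 = 7.1 points. This applies to a child with no other counted episode in that row.
- Rate, assuming 29 exposure days per child: 14 × 29 / 30.4375 = 13.34 subject-months, so one event is 7.5 per 100 subject-months. For 18 children, 17.15 subject-months and 5.8 per 100.

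**6. Person-time.** At present events and days share the same calendar span, so the rate is internally consistent. Adding a tail without changing the days would break that. From 08:00 on Day 1 to an assumed last dose at 18:30 on Day 3, plus 24 hours, is 3.44 days against the SAP's 3, about 15% longer.

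**The case against.** The strongest reply is that little is lost. For a severe episode this largely stands. A reader might infer that the DMC would be shown no severe event at all, or that its incidence and rate appear nowhere. The documents do not support that: the serious-TEAE table and two listings in the same package carry it, and if it leads to discontinuation it also enters Table 14.3.1.8. What remains is an inconsistency between two tables, plus the non-severe case.

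The windows for AEs and hypoglycaemia are also meant to differ; SAP 5.8 says that observation time is defined differently for them. That explains a shorter window. It does not explain a cut at midnight, which separates episodes by the clock and not by time since dose.

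A reader might also infer that pre-treatment nights materially contaminate the counts. Protocol 12.1.2 argues against this. Staff confirm a fast of at least 8 hours, and glucose must be at least 80 mg/dL to proceed. An episode at 02:00 treated with carbohydrate would break the fast before an 08:00 dose. What is left is mainly a low reading that recovers untreated, or an episode soon after midnight with a late-morning dose.

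Basal insulin may cause an after-midnight episode. That is fair, but on every other night the table counts such episodes whatever their cause, so attribution cannot justify dropping the last one.

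Finally, a long tail can take in time on replacement insulin, since a prandial insulin prescription is given at Visit 15 or early termination. That stands and shapes the fix.

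**Conclusion.** The point holds as a defect in the summary outputs, not as concealment of events. The exclusion follows directly from SAP 8.3.3 and 5.5. It requires that no AFREZZA dose is taken on or after the date of the episode. A child who interrupts and resumes loses nothing, and neither does a completer who doses on the morning of Visit 15.

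One affected child moves a cohort percentage by 5.6 or 7.1 points. The documents give no basis for predicting how many children will be affected; it may be none. The case for correcting the rule is that the loss is tied to stopping treatment and falls on a named safety endpoint. The existing rate calculation has no numerator–denominator mismatch, and the Day 1 effect is real but minor.

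**What to change.** In SAP 8.3.3, for the tables and both figures:

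- Define on-treatment by date and time: onset at or after the time of the first dose, and no later than a pre-specified number of hours after the last dose.
- Choose that number so that it covers the night after an evening dose. A 4-hour tail may be too short: after a 19:00 dose it ends at 23:00 and would drop a 23:30 episode that is counted now.
- Compute observation time over the same window.
- If onset time is missing, include an event dated the day after the last dose. State also how a Day 1 event without a time is classified.
- Flag in the listing any event that starts after replacement prandial insulin was begun.

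No new data should be needed. The Day 1 dosing time is in the e-CRF (SAP Table 3), later dose times are in the e-Diary (Protocol 9.2.8), and the time-profile figure already depends on event times. The cost is SAP wording and programming, and the reported counts may rise slightly.

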5.4 Study Period

Two study periods are defined: an approximately 4-week titration period (Visit 2 – Visit 16, including PK assessments at Day 1) followed by an optional 52-week extension period (Visit 17 – Visit 29). Participants in the titration period are defined as subjects who take at least one dose of study drug in the titration period and participants in the extension period are defined as subjects who complete the titration period and opt to participate in the extension study.

Start date of the titration period is defined as Study Day 1. For subjects who do not participate in the extension period, end date of the titration period is defined as the last visit/contact date; for

subjects who participate in the extension period, end date of the titration period is defined as the date of Visit 15.

Start and end date of the extension period are defined for subjects who participate in the extension period only. Start date is defined as date of Visit 15 +1 day, and end date is defined as the last visit/contact date.

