The last interval in each study period, i.e., Week 4 for the titration period and Month 12 for the extension period, will extend to the treatment end date of the study period, for subjects whose treatment duration is longer than 4 weeks or 12 months, for the two study periods respectively.

To derive event rate, observation time (in months) for a time interval will be calculated as

The number of days in the time interval which are between first dose date and last dose date (both inclusive)/30.4375.

Observation time will first be calculated for each individual subject, and then summed across all applicable subjects in the safety population.

- Time profile of hypoglycemic events in relation to pre-meal dosing

For each week in the titration period and each month in the extension period, event rate of hypoglycemia (in subject-month) will be calculated at 1 hour interval (i.e., [0,1] h, (1,2) h, (2, 3) h, and (3, 4h)) relative to the pre-meal insulin dosing time. A bar plot will be created with hypoglycemic events occurred following each pre-meal dose presented as a separate bar. Only hypoglycemic events occurred within 4 hours following a pre-meal dose will be included in this analysis.

To derive event rate, observation time for an hour (e.g., 0-1 h after breakfast) in a time interval (e.g., Week 1 in titration period) will be calculated as

The number of days in the time interval which are between first dose date and last dose date (both inclusive) /30.4375.

Observation time will first be calculated for each individual subject, and then summed across all applicable subjects in the safety population.

Subject Listings

For all hypoglycemic events and all severe events, detailed information of every event will be listed, by (in the order of) cohort, investigator site and subject.

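### The SAP 8.3.3 week formula puts each boundary one day early, so the first titration interval has 6 days instead of 7, and the rule from index to Week label is not stated

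*SAP*

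**What the plan says.** The graphical part of SAP 8.3.3 sets the interval width: "Event rate (in subject-month) will be calculated at 1 week interval for the titration period", with 1-month intervals in the extension. The rule for placing an event follows: "Weeks since the start of the study period will be calculated as" int((date − start + 1)/7). Months are int((date − start + 1)/30.4375). SAP 5.4 fixes the origin: "Start date of the titration period is defined as Study Day 1".

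The labels appear further on in the same section. "The last interval in each study period, i.e., Week 4 for the titration period and Month 12 for the extension period" runs on to the treatment end date for subjects treated for more than 4 weeks or 12 months. Week 1 is also used as a label: "in a time interval (e.g., Week 1 in titration period) will be calculated as". No sentence in the SAP text says how the computed index becomes one of these labels.

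Three figures are involved:
- Figure 14.3.1.1 (day profile of hypoglycemia) uses the formula directly.
- Figure 14.3.2.1 (day profile of cough) inherits it, because SAP 8.3.4 says it is built in the same way.
- Figure 14.3.1.2 (time profile relative to pre-meal dosing) is introduced by "For each week in the titration period and each month in the extension period, event rate of hypoglycemia", but its text neither repeats nor cites the formula.

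**The concern.** The day count date − start + 1 has no day 0. Dividing it by 7 and truncating makes the index step up on day 7 itself, although day 7 is the last day of the first week. The first block is then one day short and every later boundary comes one day early. The index also starts at 0, while the labels in the text run from Week 1 to Week 4.

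The two day-profile figures show how hypoglycemia and cough change after a child starts AFREZZA, so the first and last weeks are what a reader will look at. As written, those weeks do not have the planned width. Two programmers could also label the blocks differently and end the plot differently.

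**Working it through.** **Inputs**
- Planned width: 7 days (SAP 8.3.3). The last interval, Week 4, extends to the treatment end date (SAP 8.3.3).
- Origin: Study Day 1, the date of the first dose (SAP 5.1 and 5.4). Write d = date − start + 1, so d = 1 on the first day.
- Last titration dose: assumed on day 29, with range 28–30. The protocol flow chart puts Visit 15 on day 29 ± 1.
- Subjects: 14 or 18 per cohort and 46 overall (SAP 3.2). Both matter because "The following graphs will be presented by cohort and overall".
- Days per month: 30.4375 (SAP 5.8 and 8.3.3).

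**Step 1. Planned weeks.** Days 1–7, 8–14, 15–21 and 22–29, that is 7, 7, 7 and 8 days (last week 7–9 over the range).

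**Step 2. Printed index, int(d/7).** int(6/7) = 0, int(7/7) = 1, int(14/7) = 2, int(21/7) = 3, int(28/7) = 4. The blocks are days 1–6, 7–13, 14–20, 21–27 and 28 onward. The planned 7-day first interval is not reproduced.

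**Step 3. Labels** (days, with the count in brackets, to day 29)

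| Rule | No label | Week 1 | Week 2 | Week 3 | Week 4 |
|---|---|---|---|---|---|
| Planned | – | 1–7 (7) | 8–14 (7) | 15–21 (7) | 22–29 (8) |
| index + 1, capped at 4 | – | 1–6 (6) | 7–13 (7) | 14–20 (7) | 21–29 (9) |
| index as label | 1–6 (6) | 7–13 (7) | 14–20 (7) | 21–27 (7) | 28–29 (2) |

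Over the 28–30 range, Week 4 has 8–10 days in the second row and 1–3 in the third.

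- Index + 1: 3 of 29 days are in the wrong week (7, 14 and 21), each one week late. The cap keeps day 28 in Week 4.
- Index as label: 24 of 29 days differ from plan. Days 7, 14, 21, 28 and 29 are the five that agree.
- Merging index 0 into Week 1 does not help either. Week 1 then has 13 days, and 18 days are mislabelled.

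**Step 4. Effect on a plotted rate.** If all n subjects are on treatment for all k days of an interval, one event adds 30.4375/(n × k) per subject-month.
- Week 1 under index + 1, k = 6: 30.4375/84 = 0.36 (n = 14), 30.4375/108 = 0.28 (n = 18), 30.4375/276 = 0.11 (n = 46).
- Week 1 as planned, k = 7: 0.31, 0.24 and 0.09.
- Week 4 with the index as label, k = 2, n = 14: 30.4375/28 = 1.09, against 30.4375/112 = 0.27 for the planned 8 days.

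**Step 5. Months.** SAP 5.4 describes the titration period as "followed by an optional 52-week extension period", and 52 × 7 = 364 days. With index + 1, the twelve months have 30, 30, 31, 30, 31, 30, 31, 30, 30, 31, 30 and 30 days, which sum to 364. There is no boundary error. No day up to 366 is an exact multiple of 30.4375, so truncating and adding 1 is the same as rounding up. With the index as label there would be a Month 0, and Month 12 would begin only on day 366 (12 × 30.4375 = 365.25), so it would be empty at 364 days.

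**The case against.** The best defence is that SAP 8.3.3 extends Week 4 only for subjects treated beyond 4 weeks. Week 4 would otherwise end at four weeks, so it is the fourth interval and index + 1 is the natural mapping. This is fair. It makes the 2-day Week 4, the 24 mislabelled days and the empty Month 12 unlikely outcomes, and they should not carry the point. Under index + 1, though, the 6-day first week remains.

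Two further defences are partly right:
- The figure shells are separate files (SAP Appendix 4) and were not available. They may state the label, but a label cannot move a boundary set by the + 1 inside the truncation.
- The rates are plotted against elapsed time, where an index of 0 is not in itself an error, and the first three blocks cover the same days under both mappings. Programmers would therefore differ only in the label and in whether days 21–27 are joined to day 28 onward.

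Three stronger conclusions might be inferred, and the documents do not support them:
- *Days 7, 14 and 21 are misplaced whatever the mapping.* They are not. With the index as label they correctly receive 1, 2 and 3, and it is other days that are wrong. What both mappings share is the early boundary.
- *The rates are biased.* SAP 8.3.3 counts the days of the same interval in the denominator, so events and time at risk match. A Week 1 rate about 14% too low (6/7 − 1) would need a 7-day denominator with a 6-day count, which the SAP does not prescribe.
- *The month formula has the same fault.* It lacks only a stated label. The supplied protocol also lists no extension for Part 1 (Section 6.3), so this matters only for the extension that the SAP still describes.

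**Conclusion.** The point holds and is minor. The 6-day first interval follows directly from the printed formula and the stated origin, so confidence in it is high. Under the more plausible mapping, 3 of 29 days move by one week, and one event in Week 1 shifts the plotted rate by 0.36 instead of 0.31 per subject-month in a cohort of 14. The larger distortions depend on the less likely mapping.

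The sizes assume a last titration dose on day 29 (28–30) and full cohorts on treatment throughout the interval. Figures 14.3.1.1 and 14.3.2.1 are affected directly. Figure 14.3.1.2 is affected only if its weeks are taken to be the same ones. These figures are descriptive, and SAP Appendix 3 marks none of them for the DMC. No table or listing uses the formula.

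**What to change.** In SAP 8.3.3:
1. Replace the week formula by week = min(int((date − start)/7) + 1, 4). Day 7 gives int(6/7) + 1 = 1 and day 8 gives int(7/7) + 1 = 2, so the weeks to day 29 have 7, 7, 7 and 8 days.
2. For months, keep the printed index and add that the label is min(index + 1, 12). This is a clarification only. The week correction should not be copied across: it would give a 31-day Month 1 and a 29-day Month 12 over 364 days.
3. State in the time-profile bullet that it uses the same week and month intervals, so that all three figures agree.

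The cost is one corrected formula, one sentence on labels and one cross-reference, carried into the figure programs and checked against the shells. No new data are needed, and no table or listing changes.
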